Other Analyses 1. Baseline characteristics 2. Disposition status 3. Adherence 4. Age of Blood in relation to 90 day composite endpoint, wound Infection, and pneumonia 5. Time-to-event analyses for primary and secondary endpoints	1. Student t or Wilcoxon test, Pearson chi-square or Fisher test, 2. Pearson chi-square test 3. Pearson chi-square test 4. Pearson chi-square tests and Logistic regression 5. Log-rank test and Cox regression	1. PROC TTEST, PROC FREQ, PROC NP1WAY 2. PROC FREQ 3. PROC FREQ 4. PROC FREQ, PROC GENMOD 5. PROC LIFETEST, PROC PHREG

F. Criteria for Study Termination

There will be three interim analysis of the primary outcome measure performed in the study when 25%, 50%, 75% of the planned participants completed their participation in the study. If analysis of the primary outcome rates at the time of interim analysis indicates that the null hypothesis can be rejected the study will be recommended for termination for safety reasons.

G. Handling of Missing Data

Every effort will be made to minimize the occurrence of missing data, particularly for the primary and main secondary outcome measures. For the primary outcome, every effort will be made to contact the participants over the phone until participant termination. In the event of a potential drop out, every effort will be made to capture the primary outcome data from the VA databases. For participants who drop out during the study, multiple imputation (MI) method may be used for certain endpoint analyses. Multiple imputations will be based on Rubin's procedure using SAS PROC MI and PROC MIANALYZE. Sensitivity analysis will be performed to compare the results from the imputed data and the complete data without imputation.

H. Reporting of Any Deviations from the Original Statistical Plan

A more detailed statistical analysis plan (SAP) will be generated which will include the details of each statistical analysis plan for each outcome measure along with the suggested table shells for any reports that will be produced during the study and at the end of the study. Any deviations in the statistical plan from the protocol will be specified in the SAP. Any deviations from the SAP will be specified in a revised main manuscript which will be prepared and published at the end of the study.

XVII. STUDY ORGANIZATION AND ADMINISTRATION

A. Requirements for Participating Medical Centers

All participating medical centers must be willing and able to adhere to the study protocol. Minimum requirements for participating medical centers will include:

1. Local Site Investigator. The local site investigator will be an individual with a clinical degree (e.g. psychologist, psychiatrist, nurse) who agrees to support the study enthusiastically and devote sufficient time and energy to ensure that recruitment goals are achieved and that study participants are followed appropriately. The Site Investigator will have at least a 5/8 VA appointment.
2. Study Coordinator. The Site Investigator will recruit a Study Coordinator to assist in all aspects of study conduct including recruitment, participant monitoring, and assistance with all study procedures. The Site Investigator will make all efforts to ensure that the chosen Study Coordinator is competent and enthusiastic. Experience in the conduct of clinical investigation is highly desirable. The Study Coordinator is expected to work diligently with the Site Investigator to meet the goals of the study. In addition, the Study Coordinator will be expected to work collaboratively with the staff at the Chairman's office and the CSPCC.
3. Administrative Support. Each site must provide a letter from the Director and/or the Chief of Staff ensuring that its Site Investigator will receive full administrative support during the conduct of this study.
4. Local Approvals and Reporting Requirements. Sites will be required to agree to allow the VA Central IRB to be the primary IRB for the study and agree to use the VA Central IRB's informed consent template updated only for site specific items in the template (e.g., names of the Site Investigator). Site Investigators will be responsible for coordinating the medical center's interactions with the VA Central IRB. All sites will require Research and Development Committee approval of the study, and some sites may still require local IRB approval. The Site Investigator will be responsible for obtaining initial approval for the protocol and the informed consent form from his/her VA medical center's Research and Development Committee and from the Human Studies Subcommittee/IRB. Copies of the minutes for the meeting documenting approval by these committees or a letter from the Chair of the appropriate Committee stating when the Committee met, what their concerns were, and their final recommendation, will be submitted to the CSPCC before any participants are enrolled at the local center. It will be the responsibility of the Site Investigator to maintain continuing approval of the protocol

at the local site. Documentation of this continuing approval will be submitted to the CSPCC.

5. Global Monitoring and Reporting Responsibilities Delegated. By agreeing to participate in the study, centers delegate responsibility for global monitoring of the ongoing study to the VA Central IRB, DMC, HRC, CSSEC, CSPCC, and the CSPCRPCC. In addition, the local Research and Development Committee and the local Human Studies Subcommittee/IRB will require the Site Investigator to submit annual reports concerning the status of the study for local monitoring purposes.

B. Study Management

CSPCC: The Perry Point Cooperative Studies Program Coordinating Center (CSPCC), located in Perry Point, Maryland, will provide administrative, data processing, and statistical support for the study. All data forms will be submitted to the CSPCC for processing. The CSPCC will edit the data and create the study database. The CSPCC staff will provide guidance on completion of forms, including SAE reports. All reports during the ongoing phase of the study and the final statistical analyses will be the responsibility of the CSPCC. The CSPCC staff will also monitor study progress to ensure that the study is proceeding as scheduled. This team will be headed by the study biostatistician and will include a CSPCC project manager, a statistical programmer, a database programmer, two computer assistants, and a quality assurance nurse.

Office of the Chairman: Chairs will be in routine contact with the participating centers to ensure that the study is performed in accordance with the protocol and to encourage the local study team to keep recruitment and follow-up activities on schedule. The Study Chairman will preside over all meetings of study participants and will represent the study, along with the study biostatistician, at all meetings of outside review committees. The Chairman's Office will be funded with a full-time National Study Coordinator (1.0 FTE).

National Study Coordinator: The National Study Coordinator is responsible for maintaining enthusiasm for the study at all sites, discussing problems of mutual interest related to the study, and identifying any procedural/definitional modifications that might be required. The National Study Coordinator will be responsible to oversee all study activities in the Chairman's Office on a day-to-day operational basis. Specifically, the National Study Coordinator will:

1. Assist the Study Chairpersons in coordinating and administering all aspects of the study;
2. Assist the Study Chairpersons in monitoring the progress of the study;
3. Maintain close contact with the participating investigators/local study research Site Coordinators and assist them in any procedural details of the study;
4. Maintain close contact with the study's supervisory committees; and
5. Work collaboratively with the Perry Point CSP Coordinating Center team to organize and plan periodic meetings of participating investigators for the purposes of reporting progress of the study.

The CSP Clinical Research Pharmacy Coordinating Center (CSPCRPCC): is responsible for monitoring and reporting the safety of trial participants through the review, assessment, and

communication of serious adverse events and serious adverse events reported by study personnel. The CSPCRPCC's responsibilities occur through ongoing communication with the Study Chairman, Executive Committee, Perry Point CSPCC, and CSP Central Office. The reporting activities include the filing of regulatory documents involving adverse events to meet applicable federal regulations and CSP policies. In conjunction with the Perry Point CSPCC, the CSPCRPCC prepares reports safety data for various committees including the Data Monitoring Committee, the IRB, Executive Committee, and the study group. If any new hazards occurs, the CSPCRPCC will prepare and send an approved document to notify all site investigators within after the conference call of the identification of the new safety information.

Endpoint Committee: The Endpoint Committee is a group of experts comprised of a cardiologist, a surgeon, a nephrologist, and an internal medicine/cardiology physician. The committee is responsible for the endpoint outcome measure adjudication.

Study Sites: The Site Investigator at each of the participating medical centers will be responsible for all aspects of the study at his/her site. This includes participant recruitment and follow-up, obtaining initial and yearly local R&D Committee and IRB approvals, ensuring adequate coverage for the study in his/her absence or the absence of other study participating staff, and ensuring the integrity of the study protocol and data from his/her site. A Study Coordinator will be funded for each site and the Site Investigator will be responsible for hiring and supervising this person. In no case should any local Study Coordinator be assigned duties not related to this study. The primary goal for this position is successful recruitment, explaining informed consent, gathering data, and coordination of follow-up assessments. Funding for this position may be terminated or reduced if insufficient participants are recruited and/or data collection and follow-up are deemed to be unsatisfactory. Each Study Coordinator will work with the National Study Coordinator (located at the Study Chairman's office) to develop and to implement a recruitment plan. The Study Coordinator at the sites will participate in periodic conference calls with the other Study Coordinators and study staff.

C. Monitoring of the Study

1. Monitoring bodies

The groups charged with monitoring the various aspects of the study will be the Executive Committee, the Data Monitoring Committee (DMC), the VA's Central IRB, and the Perry Point Human Rights Committee. These committees will meet at regular intervals according to the current Cooperative Studies Program guidelines: prior to the beginning of participant intake and at least every twelve months thereafter. In addition, the CSP Site Monitoring, Auditing and Resource Team (SMART), located at the CSP Clinical Research Pharmacy Coordinating Center (CSPCRPCC), will monitor the trial for GCP compliance.

The **Executive Committee** is chaired by the Principal Proponent and consists of the study Biostatisticians, study Project Manager, study Research Pharmacist, selected participating investigators, and expert consultants. The Executive Committee is concerned with overall study management and is the decision-making body for the operational aspects of the study. The Executive Committee monitors the performance of participating medical centers and quality of

data collected, plans the publications, and oversees the publication and presentation of all data from the study. The Executive Committee must grant permission before any study data may be used for presentation or publication. This committee meets by conference call typically on a monthly basis to review the study progress and meets every 12 months to review blinded study data, decide upon changes in the study, determine the fate of sites whose performance is substandard, initiate any sub-protocols, and discuss publication of the study results.

The Data Monitoring Committee (DMC) will review the progress of the study and will monitor participant intake, outcomes, adverse events, and other issues related to participant safety. The DMC makes recommendations to the Director of the Clinical Science Research and Development (CSRD) Service about whether the study should continue or be stopped. The DMC will include experts in clinical trials, biostatistics, and ethics. These experts will not be participants in the trial and will not have participated in the planning of the protocol. The DMC will consider safety or other circumstances as grounds for early termination, including either compelling internal or external evidence of treatment differences or the unfeasibility of addressing the study hypothesis (e.g., poor participant intake, poor adherence to the protocol).

At each of its meetings during the study period, the DMC will review the randomization rates and assess the difference between the actual and the projected rates, as well as the impact of these assessments on overall trial size. If the study recruitment is inadequate, the reasons for exclusion may be scrutinized and actions may be suggested. An assessment of whether the trial should be continued will be made followed by recommendations, as appropriate. All serious adverse events will be reported on a regular basis to the DMC for their review. Unexpected serious adverse events will be reported to the DMC as soon as they become known based upon the consensus of the Study Chair, the Study Biostatistician, the Director, Perry Point CSPCC, and the Study Pharmacist. The Study Biostatistician will provide the appropriate data to the DMC at specified intervals for this purpose. Conditional power estimates will be provided to the DMC to assist them in making their decisions and recommendations.

As an independent oversight committee, DMC will be monitoring study progress at predetermined time points over the entire duration of the study. The committee will receive analyses of the study recruitment status, demographics of recruited participants, adverse effects, and study protocol adherence on a routine basis. In general, this committee will meet at six to nine months after the start of subject recruitment and yearly thereafter. The committee will receive reports about three weeks prior to their annual meetings and at six-month intervals in between the annual meetings. In order for the DMC to make its recommendation for continuation of the study, it will be necessary for them to see the analyses for the primary outcome measure annually. Periodic monitoring of interim results can significantly affect the probability of making an incorrect decision. A number of formal techniques have been developed for interpreting interim results and the DMC will review these options at their first meeting and prior to the start of data collection. For this study, a Haybittle-Peto interim analysis is proposed. The detailed analysis is described in the biostatistical research and data processing procedure/statistical analysis plan.

The VA's Central IRB will be the study's primary IRB and the IRB of record for the study. It will be responsible for the initial and continuing IRB reviews of the study. The VA Central IRB Transfusion Trigger after Operations in High Cardiac Risk Patients (TOP)

Version Number: 11 Date: 12/18/2024

must review and approve amendments (changes to inclusion/exclusion criteria, protocols, informed consents, etc), deviations, and review reports about adverse events and problems, complaints, terminations, etc. and that the investigation must provide the VA Central IRB all supporting documentation. The CSPCC will be responsible for providing the VA Central IRB with all materials that are required for each review and to respond to the VA Central IRB's queries and requests for additional materials. The VA Central IRB approves the original informed consent template and any requested changes to the informed consent forms.

The Human Rights Committee (HRC) at the Coordinating Center may be asked to convene if there is any serious adverse event requiring its attention.

Site Monitoring Auditing & Resource Team (SMART) will conduct an initial site visit at each site soon after study start-up. Additional monitoring visits may be conducted as deemed necessary by study leadership or SMART. Monitoring of sites participating in the trial will be executed according to Cooperative Studies Program (CSP) guidelines. Independent routine audits will be conducted at one or more sites per year as determined by SMART. For-cause audits will be conducted as requested by study leadership or the VA CSP Central Office. These audits may be scheduled or unannounced.

The Study Group, which consists of all participating investigators and study coordinators, will meet annually to discuss the progress of the study and any problems encountered during the conduct of the trial.

D. Monitoring data quality and protocol adherence

By utilizing Risk Based Monitoring (RBM), CSPCC will remotely monitor the study team. Each participating site's performances and data quality, completeness of follow-up and adherence to the protocol will continuously be measured. Regularly scheduled conference calls (at least monthly) with the sites, CSPCC and Chairman's office will be held to address data collection, protocol procedures and other issues. Strict adherence to the protocol will be expected of every participating center and will be monitored by the DMC, the Executive Committee, and the CSPCC. Documentation of protocol breaches will be required and any medical center with repeated protocol violations will be recommended to the Executive Committee for termination. If a participating site investigator feels that adherence to the protocol will in any way be detrimental to a particular participant's health or well-being, the interest of the participant must take precedence. In addition, CSPCC, the Executive Committee and the DMC will monitor protocol adherence centrally. The Executive Committee will consider recommending a for-cause GCP audit be conducted by SMART for any site with repeated protocol violations and will consider terminating the site from the trial.

Data quality and the completeness of data retrieval will be closely monitored on an ongoing basis by the Coordinating Center. The study biostatisticians will present interim monitoring reports to the Executive Committee and the DMC that will include the following types of information:

- Participant intake
- Randomization errors
- Breaches of protocol
- Adherence and compliance with original treatment assignment

- Missed study visits
- Completeness of follow-up
- Data quality: data query and error rates
- Audit and site visit results.

If a site is identified as an outlier in terms of data quality, a site conference call or site visit will be initiated to assess the reasons why problems are occurring and how they can be corrected. If the problems continue, the site may be placed on probation or terminated from the study.

E. Monitoring of safety, efficacy and futility

Trial safety will be monitored by CSPCC and the CSPCRPCC, and the Study Chair's Office throughout the study. Safety reports will be submitted to the DMC approximately every 6 months after recruitment begins, or more frequently, if requested by the DMC. For reports to the DMC closed session, serious adverse events will be summarized by treatment groups, and relatedness to the assigned interventions.

The DMC will review the accumulating data and be responsible for determining whether or not to recommend that the trial be stopped for efficacy, futility or safety. Data summaries will be prepared for the DMC for these purposes. Frequent summaries of serious adverse events will be prepared for the DMC for the monitoring of safety, i.e., at least semi-annually. To aid the DMC in their deliberations, other relevant information inside (e.g., secondary analyses) and outside (e.g., other studies) will be made available. Complete details of the interim monitoring plans for the study are given in Section XI: Biostatistical Considerations.

XVIII. PUBLICATIONS

A. Publication of Research Results

It is the policy of the Cooperative Studies Program not to reveal outcome data to participating investigators until the data collection phase of the study is complete. This policy is meant to prevent possible biases that might affect data collection. Members of the DMC and the CSPCC Human Rights Committee will be reviewing outcome results to ensure that the study will be terminated early if a treatment is identified as prohibitively dangerous or if a definitive answer is reached prior to the scheduled study termination date.

All presentations and publications resulting from this study will follow CSP policy as specified by the CSP guidelines. The presentation or publication of any or all data collected by participating investigators on participants entered into a Department of Veterans Affairs Cooperative Study is under the direct control of the study's Executive Committee. No individual participating investigator has the right to use this study's data to perform analyses or interpretations, or to make public presentations or seek publication of any or all of the data without the specific approval of the Executive Committee.

The Executive Committee has the authority to establish any number of publication committees, which usually will comprise subgroups of participating investigators and some members of the

Executive Committee, for the purpose of producing manuscripts for presentation and publication. Any presentation or publication related to this study should be circulated to participating investigators for review, comments and suggestions at least four weeks prior to submission of the manuscript to the presenting or publishing body.

All publications must give proper recognition to the funding source and should list all study personnel(not necessarily as authors of the manuscript). If an investigator's major salary support and/or commitment is from the VA, it is obligatory that the investigator lists the VA as his/her primary institutional affiliation. Submission of manuscripts or abstracts must follow the usual VA policy; ideally, a subtitle states, "A Department of Veterans Affairs Cooperative Study." The CSP also requires that every manuscript be reviewed and approved by the CSPCC Director prior to submission as a final quality control step. Mechanisms for appeal by a dissatisfied investigator will follow procedures defined by the VA Office of Research and Development.

Participation in Department of Veterans Affairs Cooperative Studies is voluntary. Any investigator who cannot accept these operation guidelines regarding publication policy should not volunteer to participate in the study.

B. Planned Publications

Upon completion of the study, manuscripts will be prepared that focuses on the following objectives:

- Primary publication: Upon completion of the study, a manuscript will be prepared that focuses on the primary outcome, i.e. liberal vs. restrictive composite rates of 90 day all-cause mortality, MI, acute renal failure, coronary revascularization or stroke.

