The main outcome of this analysis was defined a-priori to be the same with the one of the proposed trial, and consisted of a composite of all-cause mortality, MI, acute renal failure, coronary revascularization (either percutaneous coronary intervention or open coronary artery bypass), or stroke, within 90 days from the index operation. Mortality was defined as death from any cause and was ascertained from the Vital Status patient file. MI was defined as a serum troponin I of at least 1ng/ml that was upwards trending in patients who either a) did not have elevated troponin preoperatively, or b) did not have any preoperative troponin I check. Clinicians do not routinely order postoperative troponin; thus, we assumed that that test was requested in patients with either EKG findings or symptomatology suggestive of MI, satisfying the Third Universal Definition. Although the 99th percentile upper reference limit of troponin I is 0.06 ng/ml or less for most assays used, we employed a more conservative cutoff of 1ng/ml to minimize overestimation of the endpoint by patients who might have had mild troponin elevation from non-ischemic causes. Acute renal failure was defined as acute kidney injury (AKI) stage 3 according to RIFLE criteria (serum creatinine at least > x3 of baseline, or serum creatinine > 4 mg/dl and rise > 0.5 from baseline). The creatinine value just prior to the date of the index operation was considered as baseline for those calculations. Urine output criteria are also included in the RIFLE classification; however, urine output cannot be reliably determined from a database review, and for this reason our assessment of AKI stage 3 from this analysis may have been conservative. Coronary revascularization was ascertained using appropriate CPT codes for either percutaneous or open coronary interventions. Finally, we attempted to identify postoperative stroke using the ICD-9 code 997.5; however, this return no events. Unlike the rest of the outcomes, extracting reliable stroke rates from the CDW database is not straightforward. Furthermore, single institution data have shown the 90 day stroke rate after vascular interventions to be low (approximately 1%), which is possibly why the database query returned Transfusion Trigger after Operations in High Cardiac Risk Patients (TOP)

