no events. We stratified the patients as being high risk for cardiac events if they had history of IHD, peripheral artery disease (PAD), or underwent a PAD-related operation. We ultimately collected information on 171,357 patients who underwent the target operations and were included in our analysis.

FIGURE 2. Probability of the Composite Endpoint at Various Levels of the Postoperative Nadir Hb – Multicenter data

Similarly to the single institutional analysis, a strong association was seen between increasing values of nadir postoperative Hb and freedom from the composite endpoint (OR: 0.566, 95% CI: 0.561 to 0.57, Figure 2). From the initial patient pool, 38,153 patients were at high risk for cardiac events and dropped their nadir postoperative Hemoglobin in the early postoperative period below 10 gm/dl, conditions that would make them eligible for the proposed trial. In this high cardiac risk patient population, the composite outcome occurred in almost 30% of patients with nadir Hb between 6-9 gm/dl (a subset that will represent the restrictive transfusion arm in the proposed study) and in 15% of patients with nadir Hb between 9-10 gm/dl (a subset that will represent the liberal transfusion arm in the proposed trial). Event rates for the composite and individual endpoints are summarized in TABLE 2 below:

TABLE 2. Composite Event Rates and Individual Event Rates among Veterans at High Cardiac Risks after a Surgical Procedure

Nadir Hb	Composite Endpoint	Death	MI	ARF	Coronary Revascularization
6-9 gm/dl	29.5%	15.3%	11.0 %	11.1%	0.4%
9-10 gm/dl	15.0%	6.9%	6.2%	4.1%	0.3%

III. SIGNIFICANCE AND RELEVANCE TO VETERANS

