Objective: To examine the effect of transfusion strategies on the components of the primary endpoint.

Hypotheses: A smaller proportion of participants receiving blood under a liberal transfusion strategy will experience post-randomization death from any cause, MI, coronary revascularization, acute renal failure, or post-randomization stroke, compared to participants under restrictive transfusion strategy at 90 days after randomization.

V. STUDY OUTCOME MEASURES

A. Primary Outcome

The primary outcome is defined as a composite endpoint of all-cause post-randomization mortality, myocardial infarction (MI), coronary revascularization, acute renal failure, or post-randomization ischemic stroke up to 90 days after randomization.

MI will be defined using the Third Universal Definition of Myocardial Infarction.³⁴ (Please see Appendix I.)

Acute renal failure will be defined as Acute Kidney Injury stage III according to RIFLE criteria: Serum creatinine rise greater than 3 times that of baseline creatinine; or if baseline serum creatinine is greater than 4 mg/dl, then rise more than 0.5 mg/dl compared to baseline; or urine output less than 0.3ml/Kg/hr for 24 hours; or anuria for 12 hours. Baseline creatinine will be considered the creatinine upon admission prior to the index operation. The above urine output criteria will be only used for patients who are in the ICU and have precise monitoring of their urinary output. For patients on the surgical floor only serum creatinine changes will be used for assessment of this endpoint.

Coronary revascularization will be defined as a coronary artery bypass graft, or percutaneous coronary intervention (either angioplasty or stenting).

Stroke will be defined as new unilateral neurological deficit that lasts for more than 24 hours, and is confirmed by a brain imaging modality (either computed tomography or magnetic resonance imaging study) demonstrating new brain infarct.

B. Secondary Outcomes

Outcome 1: A composite endpoint of post-randomization infectious complications at 90 days post-randomization: Infectious complications will include wound infections, pneumonia, and sepsis.

Wound infection will be defined according to the Centers for Disease Control and Prevention (CDC) guidelines as a) positive wound culture, or b) drainage of pus from a wound, or c) suspicion of wound infection that was drained operatively.

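### The creatinine criterion for acute renal failure literally needs a value above 4 times baseline, but the planning analysis said to share its outcome used above 3 times

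*Protocol*

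**What the plan says.** Protocol V.A opens the component with "Acute renal failure will be defined as Acute Kidney Injury stage III according to RIFLE criteria" and then spells out the rule. The first creatinine criterion is "Serum creatinine rise greater than 3 times that of baseline creatinine". The second is "if baseline serum creatinine is greater than 4 mg/dl, then rise more than 0.5 mg/dl compared to baseline". Urine-output criteria follow, but they are limited to ICU patients with precise monitoring; on the surgical floor only creatinine counts. SAP 3.2.1 repeats the rule.

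Protocol II(c) describes the database analysis behind the assumed control rate. It says "The main outcome of this analysis was defined a-priori to be the same with the one of the proposed trial". Its renal failure rule carries the same RIFLE stage 3 label but reads "serum creatinine at least > x3 of baseline, or serum creatinine > 4 mg/dl and rise > 0.5 from baseline".

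Protocol XVI.A takes the 30% restrictive-arm rate from that analysis. XVI.B builds the sample size on it, and SAP 4.5 repeats both.

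**The concern.** The two rules share a label and a stated intent but not a threshold. One is written as an increment over baseline and the other as a level. In the trial rule the next criterion, "then rise more than 0.5 mg/dl compared to baseline", can only mean an increment, which makes it natural to read 'rise' as an increment in the first criterion too.

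Renal failure is one of the three large components of the composite. It also enters the 30-day secondary composite and is a tertiary endpoint of its own. Participants who peak between 3 and 4 times baseline would count or not count depending on how the sentence is read. On the surgical floor no urine-output criterion can pick them up. If readers of the rule differ, like cases are classified differently. If all follow the literal words, the component is narrower than the one used for planning.

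**Working it through.** **1. What the words require.** Let b be baseline creatinine and v the later value.
- Trial, literal: v − b > 3b, so v > 4b.
- Planning: v > 3b, or v > 4 mg/dl with v − b > 0.5 mg/dl.
- Trial, 4 mg/dl criterion: available only if b > 4 mg/dl, then v − b > 0.5 mg/dl.

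Value needed to qualify on creatinine (mg/dl):

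| Baseline | Planning | Trial, literal | Trial, read as 3 times baseline |
|---|---|---|---|
| 1.0 | > 3.0 | > 4.0 | > 3.0 |
| 1.2 | > 3.6 | > 4.8 | > 3.6 |
| 2.0 | > 4.0 | > 8.0 | > 6.0 |
| 3.5 | > 4.0 | > 14.0 | > 10.5 |
| 4.5 | > 5.0 | > 5.0 | > 5.0 |

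The last column shows a second mismatch. Even when 'rise' is read as a level, the trial rule is narrower than planning for baselines from about 1.33 mg/dl (4/3) up to 4 mg/dl, because it applies the 4 mg/dl condition to the baseline and not to the later value.

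**2. The plan's own sample size.** Inputs from Protocol XVI.B: 30% against 22.5%, two-sided 5%, 90% power. With the pooled-variance formula, p̄ = 0.2625:

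n per arm = [1.960·√(2 × 0.2625 × 0.7375) + 1.282·√(0.30 × 0.70 + 0.225 × 0.775)]² / 0.075² = 722 after rounding up.

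The total is 1444, and 1444/0.95 = 1520. Both stated figures reproduce, so the arithmetic is sound. What is open is whether the endpoint as written matches the rate put into it.

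**3. How much of the composite rests on renal failure alone.** Protocol Table 2, nadir Hb 6-9 gm/dl: composite 29.5%, death 15.3%, MI 11.0%, renal failure 11.1%, coronary revascularization 0.4%.
- Minimum: 29.5 − (15.3 + 11.0 + 0.4) = 2.8 points.
- Maximum: 11.1 points, if no renal failure patient had another component event.

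**4. Illustration only.** The documents do not say what share of planning events would fail the literal rule. Assume 25% to 50% of the sole-event cases drop out, the 25% relative reduction holds, and nothing else differs between planning and trial. With 722 per arm:

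| Sole-event points | Share lost (assumed) | Restrictive rate | Power | Total N for 90% |
|---|---|---|---|---|
| 2.8 | 25% | 30 − 0.70 = 29.3% | 89.1% | 1490 |
| 2.8 | 50% | 30 − 1.40 = 28.6% | 88.1% | 1540 |
| 11.1 | 25% | 30 − 2.78 = 27.2% | 86.0% | 1644 |
| 11.1 | 50% | 30 − 5.55 = 24.5% | 80.9% | 1888 |

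The bottom rows need every renal failure to be a sole event, which is an extreme case.

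**The case against.** The documents themselves point to the intended meaning. The criterion paraphrases a named standard, and Protocol II(c) renders the same RIFLE stage as a level of 3 times baseline and says the outcomes match. 'Rise' may be loose for 'rise to'. Protocol XVII.B puts a nephrologist on the Endpoint Committee, which may well apply 3 times baseline. This stands as evidence of intent. It does not make the written rule say so, and it is a reason to correct the wording.

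A reader might infer that the control rate will fall below 30% and the trial will lose power. The documents do not support that, because other differences push the composite up:
- The planning query found no strokes, while the trial counts them; Protocol II(c) cites about 1% at 90 days after vascular interventions.
- Planning had no urine-output data; the trial adds that criterion in ICU.
- Planning MI needed troponin I of at least 1 ng/ml on tests that clinicians chose to order. The trial uses the Third Universal Definition with troponin scheduled on days 1 to 4 and 7 (Protocol X).

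The net direction is unknown. The feasibility phase (Protocol XVI.D) is also meant to confirm the control proportion.

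A reader might also infer that adjudicators are working to 4 times baseline. No adjudication charter or instruction is among the documents, so this is not known. Nor is bias between arms shown: one rule serves both, and the committee is blinded to allocation.

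**Conclusion.** The point holds as a conflict between the written endpoint rule and the planning rule it was stated to match. On the literal words, a peak above 3 and up to 4 times baseline counted in planning and does not meet the trial's first creatinine criterion. Undercounting or inconsistent classification of renal failure is therefore possible, but not demonstrated.

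Its size cannot be fixed from the documents. The firm figures are the 11.1% renal failure rate and the 2.8 to 11.1 points of the composite that rest on it alone. These bounds use Table 2; Protocol XVI.A gives the composite as 29.8%, which would move the minimum to 29.8 − 26.7 = 3.1 and change nothing of substance. The 81% to 89% power range is conditional on an assumed loss with no offset, and should not be read as an estimate of the trial's power. The stated 1444 and 1520 are correct for their inputs.

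**What to change.** In Protocol V.A and SAP 3.2.1, write the first creatinine criterion as *serum creatinine greater than 3 times the baseline creatinine*.

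In the same edit, reconcile the 4 mg/dl criterion with Protocol II(c): state whether 4 mg/dl refers to the baseline or to the later value. Changing the first criterion alone does not restore the planning rule; at a baseline of 2.0 mg/dl the trial would still need a value above 6.0, against above 4.0 in planning. If the baseline version is kept on purpose, the documents should say that the planning rate came from a wider rule.

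Put the same formula in the adjudication instructions, and apply it to every participant blind to arm. The sample size need not change.

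The cost is a short edit to each document and a re-screen of creatinine to day 90. The scheduled in-hospital values are already collected (Protocol X), but values after discharge come from record review (Protocol IX.C), so some chart work is likely. Some participants may need re-adjudication.
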